18.2. Device deficiency

A device deficiency is the inadequacy of the investigational medical device or comparator with respect to its identity, quality, durability, reliability, usability, safety, or performance. This includes malfunctions, use errors and inadequacy in the information supplied by the manufacturer including labelling.

18.3. Serious adverse events (SAE)

A serious adverse event is an adverse event that:

- Led to death,
- Led to a serious deterioration in the health of the subject, users or other persons as defined by one or more of the following:
 - 1) a life-threatening illness or injury, or
 - 2) a permanent impairment of a body structure or a body function including chronic diseases, or
 - 3) in-patient or prolonged hospitalization, or
 - 4) medical or surgical intervention to prevent life-threatening illness or injury or permanent impairment to a body structure or a body function.
- Led to foetal distress, foetal death, a congenital abnormality, or birth defect including physical or mental impairment.

This includes device deficiencies that might have led to a serious adverse event if:

- 1) Suitable action had not been taken, or
- 2) Intervention had not been made, or
- 3) Circumstances had been less fortunate.

These are handled under the serious adverse event reporting.

Planned hospitalization for a pre-existing condition, or a procedure required by the CIP, without serious deterioration in health, is not considered a serious adverse event.

18.4. Serious adverse device effect (SADE)

A serious adverse device effect is an adverse device effect that has resulted in any of the consequences characteristic of a serious adverse event.

18.5. Anticipated serious adverse device effect (ASADE)

Anticipated serious adverse device effect is any effect that by its nature, incidence, severity, or outcome has been previously identified in the risk analysis report.

18.6. Unanticipated serious adverse device effect (USADE)

An unanticipated serious adverse device effect is a serious adverse device effect which by its nature, incidence, severity, or outcome has not been identified in the current version of the risk analysis report.

18.7. Medical care of subjects

Principal investigator shall ensure that adequate medical care is provided, during and after participation in the clinical investigation, to a subject experiencing an adverse event. All ongoing ADEs, SAEs, SADEs and DDs that could have led to a SAE at subject termination will be followed until resolution. An ongoing adverse event at subject termination visit is documented as the current status for the adverse event and will not be followed up.

The subjects shall be informed of any new significant findings occurring during the clinical investigation, including the need for additional medical care that can be required, and of the nature and possible cause of any adverse events experienced.

Principal investigator shall provide the subject with the necessary instructions on proper use, handling, storage and return of the investigational device and comparator when it is used or operated by the subject.

18.8. Reporting and timelines

18.9. Investigator's reporting responsibilities

PI at each site must assess all (S)AE's that occur at his/her site.

- All serious adverse events and serious adverse device effects must be reported to sponsor within 24 hours of the site becoming aware of the event.

- A device deficiency that could have led to a serious adverse event but did not because suitable action was taken, intervention had been made or because of fortunate circumstances should be reported to sponsor within 24 hours of the site becoming aware of the event.
- New findings and/or updates in relation to already reported serious events should also be reported to sponsor within 24 hours of the site becoming aware of the event.
- Device deficiencies and all adverse device effects related to CE marked Coloplast investigational product and/or comparator must be reported to sponsor within 24 hours of becoming aware of the event.

When reporting the SAE, the relationship to the test material shall be described whether the event is considered

- **Not related**, the event has no temporal relationship with the use of the test material or the procedures.
- **Unlikely related**, the relationship with the use of the test material seems not relevant and/or the event can be reasonably explained by another cause, but additional information may be obtained.
- **Possible related**, the relationship with the use of the test material is weak but cannot be ruled out completely. Alternative causes are also possible (e.g. an underlying or concurrent illness/ clinical condition or/and an effect of another device, drug, or treatment). Cases where relatedness cannot be assessed, or no information has been obtained should also be classified as possible.
- **Probable related**, the relationship with the use of the test material seems relevant and/or the event cannot reasonably be explained by another cause, but additional information may be obtained.
- **Definitely related/Causal relationship**, the event has a temporal relationship with the test material use/application or procedures.

The investigator will assess intensity for each AE and SAE reported during the investigation and assign it to one of the following categories:

- **Mild**, the intensity of the event is mild with no further action or intervention
- **Moderate**, the intensity of the event will lead to an action or intervention to solve the event

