4.4. Intended use of the device in the clinical investigation

The test product is intended to support collection of output from a stoma and to provide a seal between the bag and baseplate.

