5.0. General

This investigation is an open-label, randomized, controlled, comparative, cross-over study with 2 test periods and 2 test sequences comparing a new 2p coupling system with SenSura Mio Click. Each test period is 21 days (± 2 days). Each subject will participate for a total of 42 days (± 4 days). The subjects will test the investigational product and the comparator in a 1:1 randomised order. A total of 50 subjects will be enrolled and

randomized to yield 40 subjects (assuming a 20% drop-out rate) who complete the study. The sample size calculation is based on at least 6 bag changes during each test period (≥ 2 changes per week).

If a potential subject is interested in participating after the first contact, a visit (visit 0) will be arranged.

The subject will receive both written and verbal information to ensure that the subject understands what was read and explained and can freely agree to participate in the investigation. During the visit, the Principal Investigator or designee will provide oral information about the investigation based on the Subject Information Form.

Before the test periods, the subjects are invited for a screening visit (V1). Subjects will be consented prior to any study procedures. Once consented, during their participation, the subjects will complete three study visits (V2, V3 and V4). The visits will be done remotely via video conference. A follow-up call will be scheduled 7 \pm 3 days after each test visit to ensure compliance with the provided product and study procedures. Additional calls may be scheduled if needed (assessed by the Principal Investigator or designee).

At every bag change the subject will be asked to complete a questionnaire via an app installed on their smartphone.

During the visits the subject will complete a questionnaire and discuss any adverse events or device deficiencies they may have had with the site personnel.

Coloplast will provide both the investigational product and the comparator product for all subjects.

If a subject experience a problem with the investigational product during the investigation, he/she should contact the investigator for advice. Subjects that cannot complete a test period with the test product may choose to use their own product (i.e., SenSura® Mio) for the remainder of the test period. However, this must be documented by the Principal Investigator.

[figure not shown]

Figure 1 Design of the investigation.

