18.1. Adverse device effect

An adverse event, which is related to the use of the investigational medical device, is an adverse device effect, and should be marked as unlikely related, possible related, probable related or with causal relationship on the adverse event form.

The definition of an adverse device effect includes any event resulting from insufficiencies or inadequacies in the instruction for use, or any malfunction of the medical device, as well as any event resulting from use error or from intentional misuse of the device.

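### Section 18.9 defines the top SAE causality grade by timing alone and the bottom grade by its absence, so the scale is not ordered

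*Combined protocol and SAP*

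**What the plan says.** Section 18.9 introduces its causality scale for serious events: "When reporting the SAE, the relationship to the test material shall be described whether the event is considered" as one of five grades.

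- The top grade, *Definitely related/Causal relationship*, applies when "the event has a temporal relationship with the test material use/application or procedures". No other condition is attached.
- The bottom grade, *Not related*, applies when "the event has no temporal relationship with the use of the test material or the procedures". Again there is no other condition.
- *Unlikely related* turns on whether the link seems relevant and/or whether "the event can be reasonably explained by another cause, but additional information may be obtained".
- *Probable related* turns on the same two considerations in the opposite direction: the link seems relevant and/or "the event cannot reasonably be explained by another cause, but additional information may be obtained".
- *Possible related* covers a weak link that cannot be excluded, and also takes cases that cannot be assessed.

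Section 18.1 defines an adverse device effect (ADE) as an adverse event related to use of the investigational device. It then says that such an event "should be marked as unlikely related, possible related, probable related or with causal relationship on the adverse event form". These are four of the five grade names, without definitions and without *Not related*.

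On exposure, section 4.4 states: "The test product is intended to support collection of output from a stoma and to provide a seal between the bag and baseplate". Section 5.0 sets two test periods of 21 days (± 2) each, and section 7.1 starts the second product at the cross-over visit. Section 4.3 uses the term investigational products for test and comparator together. Test material, the term used in 18.9, is not defined in the available text.

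**The concern.** A causality scale should become harder to satisfy as it rises. Here the two end grades use timing and the middle three use relevance and alternative causes, so the grades do not lie on one line. With an appliance worn almost throughout, timing separates very little: nearly any event in a test period coincides with use of a study product.

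What is at stake is the meaning of the device-related labels. If the written definitions are followed, background illness during wear can be recorded as definitely caused by the device. If they are overridden by judgment, the recorded grade depends on how far the investigator departs from the text. The trial is open-label and runs at one center, so no second site's reading would expose the difference. Section 10.0 summarizes assessments by product and section 5.5 lists adverse events among the safety assessments, so the labels may be read as a comparison of products.

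**Working it through.** The plan gives no figure for this point. The check is mainly of wording, with a short calculation of exposure.

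**1. Is the scale ordered?** Take an SAE with a plain external cause, such as a hospital admission after a traffic accident, occurring while the test product is worn. Read *temporal relationship* as coincidence with wear.

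| Grade in 18.9 | What the definition turns on | Met by this SAE? |
|---|---|---|
| Not related | No temporal relationship | No |
| Unlikely | Link not relevant and/or another reasonable explanation | Yes |
| Possible | Weak link that cannot be excluded, or case not assessable | No, the cause is clear |
| Probable | Link relevant and/or no other reasonable explanation | No |
| Definitely | A temporal relationship | Yes |

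The event meets the highest grade and the second lowest, fails the two between, and is barred from the lowest. *Definitely* is also easier to meet than *Probable*, since timing alone is enough. No rule in the available text says which grade prevails when two are met. Part of section 18.9 after the intensity grades is not available, and I infer nothing from that.

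**2. How much of the observation time is affected?** Inputs from section 7.1: Visit 1 on Day 1, first application on Day 3 + 2 days (Day 3, 4 or 5), Visit 4 on Day 46.

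- Visit 1 to Visit 4: 46 − 1 = 45 days.
- First application Day 3: 46 − 3 = 43 days worn, 43/45 = 96%.
- First application Day 4: 46 − 4 = 42 days worn, 42/45 = 93%.
- First application Day 5: 46 − 5 = 41 days worn, 41/45 = 91%.

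Only the 2 to 4 days before first application clearly lack a temporal relationship with use.

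**3. What if test material means the test product only?** With periods of 21 ± 2 days, the test product's share of wear is 21/(21 + 21) = 50%, ranging from 19/(19 + 23) = 45% to 23/(23 + 19) = 55%. If the procedures limb of the definition is also set aside, the same background SAE could then meet *Definitely* in the test period and *Not related* in the comparator period. The narrower meaning shortens the affected time but could build a difference between products into the grading.

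**4. Which rules depend on the grade?**

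- Not dependent: reporting of all SAEs to the sponsor within 24 hours (18.9), reporting of all SAEs to authorities (18.10), follow-up of ongoing SAEs (18.7), and the leakage analysis and pass/fail criteria (10.0, 10.3).
- Dependent for serious events: whether an SAE is labelled a serious adverse device effect (SADE, 18.4).
- Dependent for non-serious events, if the 18.9 definitions carry over to 18.1: ADE counts, follow-up to resolution (7.2, 18.7), the lists of related AEs and ADEs sent to the Medical Advisor (18.11), and the 24-hour ADE rule in 18.9, which is tied to CE marked product and/or comparator.

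**5. Sections 18.1 and 18.9 side by side.** Section 18.1 makes relatedness the condition for being an ADE, yet allows an ADE to carry *Unlikely related*, which 18.9 describes as a link that seems not relevant. The two sections do not say whether an event so graded is counted as an ADE.

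**The case against.** The strongest reply is that the scale, read as a whole, does not push events to the top. Meeting a definition is not the same as being assigned to it. An event with another reasonable explanation has an explicit place under *Unlikely*, and unassessable cases go to *Possible*. Those grades would have little use during wear if timing alone settled the matter. The top label also contains the words causal relationship, and 18.1 starts from relatedness. Any error leans towards over-attribution, and nothing in the pass/fail criteria uses causality.

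Much of this stands. A reader might infer that every event after Visit 2 must be graded *Definitely related*. The documents do not support that: the scale is introduced for SAEs only, the grades overlap without a rule favoring the highest, neither temporal relationship nor test material is defined, and section 5.0 lets a subject who cannot complete a test-product period return to their own product. A reader might also infer that causality decides which SAEs are reported within 24 hours or reach the Medical Advisor. Section 18.9 requires reporting of all SAEs, and 18.11 opens by requiring that all SAEs be provided to the Medical Advisor, although its later list narrows to related ones.

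The reply does not remove the defect at the two ends. Overlap that lets one event fit opposite grades is itself the fault, and the exclusion of *Not related* for a coincident event with a clear other cause remains on the literal wording.

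**Conclusion.** The point holds as a defect in the wording of the two end grades. It is firm for SAEs, where it affects the SADE label. For non-serious events it is an inference, because 18.1 borrows the grade names but not the definitions.

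The exposed time is 91% to 96% of the days from Visit 1 to Visit 4 if test material covers both products. If it covers the test product only, it is 45% to 55% of wear time. Both figures assume that temporal relationship means coincidence with wear and that the subject stays on study product. The number of events that would be graded differently cannot be estimated, because the visible text gives no expected adverse event rate.

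The trial's leakage conclusion does not change. The correction is worth making because the safety labels would otherwise rest on an unordered scale. Whether events graded *Unlikely* count as ADEs is a convention for the sponsor to choose; the documents do not show the inclusive choice to be wrong, only that 18.1 and 18.9 need reconciling.

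**What to change.** - In 18.9, require for *Definitely related* both a temporal relationship and that no other cause reasonably explains the event, so that it is stricter than *Probable*.
- In 18.9, let *Not related* include events clearly due to another cause even when they occur during wear.
- State whether test material covers the comparator as well as the test product.
- Say whether the 18.9 definitions also apply to non-serious events, and reconcile 18.1 with 18.9 by stating which grades are tabulated as ADEs.

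The cost is a wording change in two sections and in the adverse event form. The main downside is that fewer events will be labelled device-related, and for non-serious events that also means fewer followed to resolution or listed for the Medical Advisor. The sponsor should accept that effect knowingly when choosing the ADE convention.

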18.10. Sponsors reporting responsibilities

It is the responsibility of sponsor to ensure that the following are reported to regulatory authorities immediately, but no later than 7 calendar days following the date of awareness by sponsor.

- All serious adverse events.
- All serious device effects.
- All device deficiencies that could have led to serious adverse events but did not because suitable action was taken, intervention had been made or because of fortunate circumstances.
- New findings and/or updates in relation to already reported events.

If the serious adverse event results in imminent risk of death, serious injury, or serious illness that requires prompt remedial action for other subjects, users or other persons or a new finding to such a serious adverse event, sponsor must immediately but no later than 2 calendar days after awareness by sponsor report the event to *regulatory authorities*.

18.11. Medical Advisor Safety Review

The Sponsor is responsible for ensuring all Serious Adverse Event (s) are provided to the Medical Advisor for review and discussion.

The Medical Advisor will be informed of the following:

- All serious adverse events related to the investigation product or clinical investigation and serious adverse device effects
- A device deficiency that could have led to a serious adverse event but did not because suitable action was taken, intervention had been made or because of fortunate circumstances
- New findings and/or updates in relation to already reported serious events

In addition, the Medical Advisor will receive lists of any reported AE's and ADE's related to the investigation product or clinical investigation, as defined by sponsor for a review of safety.

Correspondence, decisions, and recommendations regarding safety in the Clinical Investigation from the Medical Advisor must be documented and saved electronically in the Sponsor File.

18.12. Data Safety and Monitoring Board (DSMB)

The review of all safety data will be conducted on an ongoing basis to identify any potential safety issues. If needed, the Medical Advisor can call for a Data Safety and Monitoring Board meeting with relevant members, to discuss potential safety issues and further recommendations, if relevant.

Based on the safety data review, the Medical Advisor along with the DSMB may recommend that the sponsor modifies, temporarily suspends, or terminates the clinical investigation.

Correspondence, decisions, and recommendations regarding safety in the Clinical Investigation from the Data Safety and Monitoring Board must be documented in meeting minutes and saved electronically in the Sponsor File.

All final decisions, however, regarding clinical investigation modifications, remain with the Sponsor.

19. Suspension or premature termination of the clinical investigation

Sponsor may suspend or prematurely terminate an investigation site or the entire clinical investigation for documented significant reasons.

If a suspicion of an unacceptable risk to subjects develops during the clinical investigation, sponsor will suspend the investigation while the risk is assessed. Sponsor will terminate the investigation if an unacceptable risk is confirmed. Sponsor will ensure that the premature termination will be justified in writing and will promptly inform the IRB. If monitoring or auditing of the clinical investigation identifies serious or repeated deviations at one of the participating investigation sites, sponsor will suspend or terminate the particular investigational site. The sponsor or investigator will inform the IRB as appropriate about the termination of the site.

If suspension or termination of the clinical investigation occurs, the investigator(s) will promptly inform the enrolled subjects. Sponsor will provide resources to fulfil the obligations from the CIP for follow-up of the subjects, as necessary.

20. Clinical investigation report

At completion of the investigation sponsor is responsible for writing the clinical investigation report. The report is retained on file. The report contains a critical evaluation of all data, which have been collected during the investigation. The report describes the methodology and design and a data analysis, including statistical preparation and conclusion.

Appendix 1: Bristol stool scale.

Only to be used for subjects with a colostomy. Subjects with a colostomy need to have liquid faecal output (type 6-7 on the Bristol stool scale).

Type 1	Type 2	Type 3	Type 4	Type 5	Type 6	Type 7
						
Separate hard lumps, like nuts (hard to pass)	Sausage-shaped but lumpy	Like a sausage but with cracks on its surface	Like a sausage or snake, smooth and soft	Soft blobs with clear-cut edges (passed easily)	Fluffy pieces with ragged edges, a mushy stool	Watery, no solid pieces, entirely liquid

Leats S, Heaton KW (1997). "Stool form scale as a useful guide to intestinal transit time".
Scand J Gastroenterol 32 (9): 920-4.

Appendix 2 – Instructions & Subject Questionnaire

The participants must be instructed in the following:

- Bag change frequency: Bags must be changed at least twice per week. Baseplates can be changed at bag change or left until next change as they choose. They are welcome to change more than twice per week. If baseplate is changed, the bag should also be changed.
- It is very important to explain to the participants what is meant by "feces having leaked out *through* the coupling" not to be confused with leakage from under baseplate that has spread to the coupling from the outside.
- Explain how to scrutinize the coupling before changing the bag. Look at it from all sides (with help of a mirror and/or smartphone where not visible to the eye). Drawings will be helpful for explaining what to look for.
- Be careful to instruct that at bag change, the coupling on the baseplate must be cleaned thoroughly so leakage of feces during wear time is not confused with feces not having been cleaned from the coupling at bag change.
- Make sure to check that the coupling is clean after bag change.
- If both bag and baseplate are changed at the same time, it is ok to take them off together as we do not ask questions related to opening of the coupling.
- Make sure participants are guided on remembering in which test period (1 or 2) they tested the new coupling when the final questions are asked at visit 3.

Overall procedure at every bag change:

- Look at the coupling from all angles before changing any of the products
- Change the bag (or bag and baseplate)
- If only a bag change is performed - remember to check that the coupling is clean after the change
- Register date and time in the app.
- Answer the questions in the app.

Questionnaire at each bag change:

- Are there any signs of feces having leaked through the coupling since last bag change? (yes/no), IF YES: How much leakage through the coupling has there been? Please choose one of the options below:

1. Small
2. Medium
3. Large

Note: Subjects will be provided with examples as reference. (Refer to appendix 3)

- Did you use any supporting accessories (yes/no) If yes, click for options (multiple choice):

1. Paste
2. Elastic barrier strips
3. Protective film
4. Deodorant
5. Adhesive remover
6. Cleanser for the skin
7. Tape around the outer edge of the adhesive
8. Moldable rings/seals
9. Belt
10. Powder
11. Skin care lotion
12. Hernia belt
13. Supporting garment
14. Other, please specify _____

- Did you change the baseplate in addition to the bag change? (Yes/no)

Additional questions at Visit 4 or at Study Termination:

[figure not shown]
[figure not shown]
[figure not shown]
(Before answering the following questions, please clarify together with your study nurse which test period you tested the new coupling)

The new coupling was tested in (The first test period/the second test period) (Click for options (only one):

How satisfied are you with the new coupling? (Click for options (only one):

1. Very satisfied
2. Satisfied
3. Dissatisfies
4. Very dissatisfied

Would you consider using the new coupling in the future? (Yes/No)

